### 9.1.2 ASAS20, 40, ASAS 5/6 response, and ASAS partial remission

The ASAS20 is defined as an improvement of at least 20% and absolute improvement of at least 1 unit on a 0 to 10 NRS in at least 3 of the 4 following domains:

- PGADA (see Section 9.1.13)
- Pain assessment (the total spinal pain NRS score)
- Function (represented by BASFI, Section 9.1.6)
- Inflammation (the mean of the BASDAI questions 5 and 6, [see Section 9.1.5] concerning morning stiffness intensity and duration)

and absence of deterioration in the potential remaining domain [deterioration is defined as a relative worsening of at least 20% and an absolute worsening of at least 1 unit].

The ASAS criteria for 40% improvement are defined as relative improvements of at least 40%, and absolute improvement of at least 2 units on a 0 to 10 NRS in at least 3 of the 4 domains and no worsening at all in the remaining domain.

The ASAS 5/6 response is defined as at least 20% improvement in 5 of 6 domains, including spinal mobility (lateral spinal flexion) and CRP as more objective measures (Brandt et al, 2004).

The ASAS partial remission response is defined as a score of  $\leq 2$  units on a 0 to 10 unit scale in all 4 domains listed above for ASAS20.

The ASAS variables will be calculated at Weeks 1, 2, 4, 8, 12, 16, 20, 24, 28, 32, 36, 40, 44, 48, 52/WD, and Week 156/SFE-WD.

### 9.1.3 ASAS-NSAID score

The ASAS-NSAID score is a tool that has been developed to measure the magnitude of NSAID intake during clinical studies (Dougados et al, 2011). In order to calculate the ASAS-NSAID score, the following information will be collected:

- Has there been NSAID intake since last visit?
- NSAID name
- Average daily intake (mg)
- Days with intake
  - <1 day/week
  - 1 to 3 days/week
  - 3 to 5 days/week
  - $\geq 5$  days/week
  - Every day
- Starting date
- End date (or ongoing)

The general formula for calculation is as follows:

- (equivalent NSAID score)  $\times$  (days of intake during period of interest)  $\times$  (days per week)/(period of interest in days)

Each of the components of the above calculation is described below:

- Equivalent NSAID score: This is reported in terms of NSAID equivalent dose in mg/day on a 0 to 100 scale where the diclofenac 150mg equivalent is set to 100. An NSAID equivalence table was developed based on a survey of ASAS members. The table including the consensus equivalence score for various NSAIDs can be found in the Statistical Analysis Plan (SAP).
- Days of intake during period of interest: Equivalent to the total number of days covered during the period that is being measured.

- Days per week: Proportion of days per week when the NSAID is taken. This is collected in the categories described in the days with intake category listed above. Each category corresponds to a score as follows (score in parentheses):
  - Every day (7/7)
  - $\geq 5$  days/week (6/7)
  - 3 to 5 days/week (4/7)
  - 1 to 3 days/week (2/7)
  - $< 1$  day/week (0.5/7)
  - No NSAID intake (0)
- Period of interest in days: Refers to the number of days covered for a given NSAID. If only 1 NSAID was taken during the period of interest, this will be the same as days of intake during period of interest.

Dougados et al 2011 provided the following example. If during a period of interest (between 2 visits) of 6 months, the subject has taken piroxicam 20mg during 4 months and if during this 4 month-period he has taken piroxicam 3 to 5 days per week the calculation is as follows:

- $100 \text{ (20mg piroxicam score)} \times 120 \text{ (4 months)} \times 4/7 \text{ (3 to 5 days/week)} / 180 \text{ (6 months)} = 38.1$

If the subject has used 10mg piroxicam during the remaining 2 months on 2 days a week, the NSAID score for this period is:

- $50 \text{ (10mg piroxicam score)} \times 60 \text{ (2 months)} \times 2/7 \text{ (1 to 3 days/week)} / 180 \text{ (6 months)} = 4.8$

In this example the total score for the 6-month period is 42.9 (38.1 plus 4.8).

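### The component definitions of the ASAS-NSAID score contradict the protocol's own formula and worked example, and the one-NSAID rule removes NSAID-free time from the score

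*Protocol*

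**What the plan says.** Section 9.1.3 multiplies an equivalent NSAID score by "days of intake during period of interest" and by the proportion of days per week on which the drug is taken, then divides by the period of interest in days. It goes on to define each component.

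- Numerator: "Days of intake during period of interest: Equivalent to the total number of days covered during the period that is being measured".
- Denominator: "Period of interest in days: Refers to the number of days covered for a given NSAID".
- Rule for a single drug, attached to the denominator: "If only 1 NSAID was taken during the period of interest, this will be the same as days of intake during period of interest".

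The worked example uses the terms differently. It begins "If during a period of interest (between 2 visits) of 6 months, the subject has taken piroxicam 20mg during 4 months", so its period of interest is the time between visits. It puts 120 days over 180 for the first regimen and 60 over 180 for the second, and it closes with "In this example the total score for the 6-month period is 42.9".

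Section 4.1.3 lists change from Baseline in the ASAS-NSAID score among the other efficacy variables. Section 9.1.3 sends only the table of equivalent doses to the SAP; the formula and its components are fixed in the protocol.

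**The concern.** The same term carries two meanings within one section. In the example the period of interest is the interval between visits; in the definition it is the time covered by a particular drug. The one-NSAID sentence then makes numerator and denominator identical, so the duration of use cancels and only dose and weekly frequency remain.

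The score is meant to measure how much NSAID a subject takes, so losing NSAID-free time matters most where intake changes. The protocol lets investigators change NSAIDs during the 52 weeks, subject to the avoidance windows in Table 7-1, so starts and stops within an interval are to be expected. Those are the intervals for which the written rule gives the wrong value. A derivation programmed from the definitions would differ from one programmed from the example, and the reported change from Baseline would differ with it.

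**Working it through.** **Inputs, all from Section 9.1.3.** Equivalent score 100 for piroxicam 20mg and 50 for 10mg; 120 days on the first regimen and 60 on the second; 180 days between visits; 4/7 for 3 to 5 days a week and 2/7 for 1 to 3 days a week.

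**Formula.** Score = equivalent score × days of intake × weekly proportion / period of interest, summed over regimens.

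**Step 1: reproduce the protocol's figure.** Use days on the drug as numerator and the interval between visits as denominator.

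- 100 × 120 × (4/7) / 180 = 38.1
- 50 × 60 × (2/7) / 180 = 4.8
- Total 42.9, as stated.

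**Step 2: apply the one-NSAID rule to the first regimen alone.** The example computes 38.1 for a subject on one NSAID for 4 of 6 months before it introduces the second regimen, so this is the protocol's own case. Denominator = days of intake, so the ratio is 1.

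- 100 × 1 × (4/7) = 57.1, against 38.1.
- 57.1 / 38.1 = 180/120 = 1.5, that is +50%.

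**Step 3: vary the days on the drug.** Same drug and frequency, 180-day interval.

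| Days on NSAID | One-NSAID rule | Example's method |
|---|---|---|
| 60 | 57.1 | 100 × 60 × (4/7) / 180 = 19.0 |
| 90 | 57.1 | 100 × 90 × (4/7) / 180 = 28.6 |
| 120 | 57.1 | 38.1 |
| 180 | 57.1 | 57.1 |

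The written rule does not respond to stopping. The two methods agree only when the drug covers the whole interval. Otherwise the overstatement factor is 180 divided by the days on the drug.

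**Step 4: apply a ratio of 1 to each line of the full example.** 100 × (4/7) + 50 × (2/7) = 57.1 + 14.3 = 71.4, against 42.9.

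**Step 5: test the correction.** With numerator = days covered by the regimen and denominator = all days between the visits, the text gives 38.1 + 4.8 = 42.9.

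**The case against.** The best defence is that the intended calculation is plain. The formula's labels are sound, two worked lines show every number, and start and end dates of each NSAID are collected, so the right score can be derived without new data. A careful programmer may simply follow the example. This stands and limits the consequence, but it does not remove the contradiction: the definitions are the operative text and they disagree with the example.

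A second defence is that the definitions can be made to yield 42.9. Piroxicam covers 120 + 60 = 180 days in all, so the days covered for that NSAID equal the example's denominator. If the numerator is taken separately for each dosing segment, the numerators are 120 and 60. This too stands, so it would be wrong to say that no reading reproduces the example. The reading works only because the two regimens together fill the interval. Without the second regimen the drug covers 120 days, the ratio becomes 1 and the score is 57.1, not the 38.1 that the protocol prints.

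A reader might infer something stronger: that the two definitions are simply reversed, and that the example would then score 100 × 180 × (4/7) / 120 + 50 × 180 × (2/7) / 60 = 85.7 + 42.9 = 128.6, beyond a 0 to 100 scale. The document does not support this. That total treats two doses of piroxicam as two NSAIDs and sets aside the one-NSAID rule. Also, the 0 to 100 range is stated for the equivalent-dose component only; no bound is given for the final score.

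**Conclusion.** The definitions in Section 9.1.3 are wrong as written, in a derivation that the protocol itself fixes. Whenever one NSAID is taken for part of an interval, the one-NSAID rule overstates the score: 57.1 instead of 38.1 (+50%) for 120 of 180 days at equivalent score 100 and 3 to 5 days a week. A subject who takes one NSAID throughout the interval is unaffected.

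The reach is modest. The score enters neither fixed testing sequence in Section 14.2 and is not among the variables listed for ANCOVA in Section 14.5. It plays no part in ASDAS-MI or ASAS40. A reader might also take it to be the trial's check on whether NSAID changes mask or exaggerate the treatment difference. The protocol nowhere gives it that role: the secondary variable on background medication counts subjects without relevant changes and is defined separately.

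The conclusion assumes that the example, which agrees with the formula's labels, shows the intended calculation. The SAP was not available, so whether its derivation follows the example or the definitions is unknown.

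**What to change.** In Section 9.1.3:

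1. Define days of intake as the days within the interval covered by that NSAID regimen.
2. Define the period of interest as the total number of days in the interval between the two visits.
3. Delete the sentence that equates the two when one NSAID is taken.
4. State that the score is summed over regimens, as the example does.

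Check that the SAP derivation uses the same definitions and returns 42.9 for the example. The cost is a few sentences of text and that one check; data collection, design and sample size do not change.

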#### 9.1.4 ASQoL

The ASQoL, a validated disease-specific 18-item questionnaire, has been developed specifically for measuring HRQoL in subjects with AS (Doward et al, 2003). The ASQoL has been used and has shown to be responsive in axSpA (Barkham et al, 2009; Haibel et al, 2008). The ASQoL score ranges from 0 to 18 with higher score indicating worse HRQoL. A change of 1.8 points, which represents 10% of the possible score range, has been used as the minimal clinically important difference (MCID) criteria to guide the interpretation of ASQoL score changes in previous trials with a TNFi (van der Heijde et al, 2009; Davis et al, 2007). A change in ASQoL score of 2 points (ie, 10% of the total score range) will be used as the MCID to guide the interpretation of ASQoL score changes (see Appendix 18.4).

The ASQoL assessments per visit are described in Table 5–1, Table 5–2, and Table 5–6.

#### 9.1.5 BASDAI

The most common instrument used to measure the disease activity of AS from the subject's perspective is the BASDAI (Garrett et al, 1994). The BASDAI is a validated self-reported instrument which consists of six 10-unit horizontal NRSs to measure severity of fatigue, spinal and peripheral joint pain and swelling, enthesitis, and morning stiffness (both severity and duration, respectively) over the last week (van Tubergen et al, 2015). The final BASDAI score

ranges from 0 to 10, with lower scores indicating lower disease activity. The MCID used to interpret scores is 10mm on a VAS or 22.5% of the Baseline score (Pavy et al, 2005). An MCID of 1 unit will be selected for the NRS version (see Appendix 18.5).

The BASDAI 50 is defined as an improvement of at least 50% in the BASDAI response.

The BASDAI is calculated as follows:

$$\frac{Q1 + Q2 + Q3 + Q4 + \left(\frac{Q5+Q6}{2}\right)}{5}$$

#### *Fatigue item of the BASDAI*

Fatigue as a major symptom of AS can effectively be measured with single-item questions such as the BASDAI item (van Tubergen et al, 2002b). This item has shown moderate to good reliability and responsiveness (van Tubergen et al, 2002b). The same MCID will be used for the fatigue item of the BASDAI as for the total BASDAI score, ie, a change of 1 unit on the NRS.

The BASDAI assessments per visit are described in the schedule of study assessments Table 5–1, Table 5–2, Table 5–3, and Table 5–6.

#### **9.1.6 BASFI**

The BASFI is a validated disease-specific instrument for assessing physical function (van der Heijde et al, 2005; Calin et al, 1994). The BASFI comprises 10 items relating to the past week. The NRS version will be used for the answering options of each item on a scale of 0 (“Easy”) to 10 (“Impossible”) (van Tubergen et al, 2015 and van Tubergen et al, 2002a). The BASFI is the mean of the 10 scores such that the total score ranges from 0 to 10, with lower scores indicating better physical function. The MCID used to interpret scores is 7mm on a 0 to 100mm VAS or 17.5% of the Baseline score (Pavy et al, 2005); an MCID of 1 unit will be used for the NRS version (see Appendix 18.6).

The BASFI assessments per visit are described in Table 5–1, Table 5–2, Table 5–3, and Table 5–6.

#### **9.1.7 BASMI**

The BASMI characterizes the spinal mobility of subjects with AS. The BASMI is a disease-specific measure consisting of 5 clinical measures to reflect subject axial status: cervical rotation; tragus to wall distance; lateral spinal flexion; modified Schober test; intermalleolar distance. Each of the 5 movements is scored according to the linear BASMI definition. The mean of the 5 scores provides the BASMI score. The higher the BASMI score the more severe the subject’s limitation of movement due to their axSpA.

The BASMI assessments per visit are described in Table 5–1 and Table 5–2.

#### **9.1.8 Enthesitis (MASES)**

The MASES is an index that measures the severity (ie, intensity and extent) of enthesitis through the assessment of 13 entheses (bilateral costochondral 1, costochondral 7, anterior superior iliac spine, posterior iliac spine, iliac crest and proximal insertion of the Achilles tendon sites, and the

fifth lumbar vertebral body spinous process) (Heuft-Dorenbosch et al, 2003) each scored as 0 or 1 and then summed for a possible score of 0 to 13.

Enthesitis assessments per visit are described in [Table 5–1](#) and [Table 5–2](#).

### **9.1.9 Extra-articular assessments**

The evolution of associated nonmusculoskeletal features including IBD, psoriasis and uveitis (including their severity) and flare rate will be assessed as described [Table 5–1](#) and [Table 5–2](#).

### **9.1.10 Health status (EQ-5D)**

The EQ-5D is comprised of a 5-item health status measures and a VAS. Each of the 5 health states is divided into 3 levels: no problem, some or moderate problems and extreme problems and is scored as 1, 2, and 3, respectively. The EQ-5D VAS records the respondent's self-rated health status on a vertical 20 cm scale, 0 to 100 graduated (0=worst imaginable health status, 100=best imaginable health status) (see Appendix 18.7).

This instrument is to be completed by the subject as described in [Table 5–1](#) and [Table 5–2](#).

### **9.1.11 MOS Sleep Scale**

The MOS Sleep Scale is a validated generic self-administered scale measuring specific aspects of sleep. The frequency with which each problem has been experienced during the previous 4 weeks is rated on a 5-point scale ranging from “none of the time” to “all of the time,” except sleep quantity, which is reported in hours. All scores are transformed linearly to range from 0 to 100, again with the exception of the sleep quantity subscale, which is scored in hours. Higher scores indicate more of the attribute implied by the scale name (eg, more sleep disturbance, more adequate sleep, and greater sleep quantity). The psychometric properties of the MOS Sleep Scale have been found to be satisfactory by Hayes and colleagues (Hays et al, 2005). The domains of interest for this study are the Sleep Disturbance and the Sleep Problems Index II domains. The MCID for the Sleep Problems Index II is 6 points on a 0 to 100 scale (Wells et al, 2007) (see Appendix 18.8).

Subjects will be asked to complete the MOS Sleep Scale as described in [Table 5–1](#) and [Table 5–2](#).

### **9.1.12 MRI assessments**

Magnetic Resonance Imaging according to the ASAS/OMERACT definition is the presence of bone marrow oedema (BMO) or osteitis highly suggestive of SpA that is located in the typical anatomical areas (subchondral or periarticular bone marrow). There must be either more than 1 BMO lesion on 1 slice or a lesion that is present on at least 2 consecutive slices (Rudwaleit et al, 2009d). In practice this is very similar to the SI joint SPARCC score  $\geq 2$  definition of MRI that requires at least 2 BMO lesions to be present. A recent paper showed that the sensitivity and specificity of the ASAS/OMERACT and SI joint SPARCC score  $\geq 2$  definitions of MRI positive were identical (sensitivity 0.80, specificity 0.76) (Weber et al, 2014). The Berlin modification of the ASspiMRI-a is a scoring system with a concentration on short-tau-inversion recovery (STIR) sequences without other fat saturation techniques (Braun and Baraliakos, 2011; Lukas et al, 2007; Braun and van der Heijde, 2002; Braun et al, 2003). This scoring method quantifies changes in 23 vertebral units (VU) of the spine (from C2 to S1). A VU is defined as the region between 2 virtual lines through the middle of each vertebra. Active inflammation is scored by

grading the degree of BMO from 0 to 3 in 1 dimension on 1 or more consecutive slices that represent the highest level of inflammation in a particular VU. Total spine ASspiMRI-a score in the Berlin modification can range from 0 to 69. In addition to the method mentioned above, MRIs may be evaluated using other reading criteria.

Magnetic resonance imaging of the spine and SI joints will be performed at Screening and at the Week 12 and at the Week 52/WD visits if MRI was performed more than 12 weeks prior to Week 52/WD. A further MRI of the SI joints will be performed at Week 156/SFE-WD. Magnetic resonance images will be assessed centrally and scoring will be done by 2 independent readers, who are blinded to both the order of the scans and to the treatment group, using a previously reported scoring system.

#### **9.1.13 PGADA (NRS)**

Subjects will score their global assessment of their disease activity in response to the question “How active was your spondylitis on average during the last week?” using a NRS where 0 is “not active” and 10 is “very active” (van Tubergen et al, 2015) (see Appendix 18.9).

The PGADA assessments per visit are described in Table 5–1, Table 5–2, Table 5–3, and Table 5–6.

#### **9.1.14 PhGADA**

The Investigator will assess the overall status of the subject with respect to the axSpA signs and symptoms and the functional capacity of the subject using a VAS where 0 is “very good, asymptomatic and no limitation of normal activities” and 100 is “very poor, very severe symptoms which are intolerable and inability to carry out all normal activities.”

This assessment by the Investigator should be blinded.

The PhGADA will be completed as described in Table 5–1, Table 5–2, and Table 5–3.

#### **9.1.15 Productivity measures (Work Productivity Survey)**

The WPS is an instrument used to assess productivity at work and within the home. The WPS has been found to be valid, reliable, and responsive to clinical changes in RA, PsA, and axSpA subjects (Osterhaus and Purcaru, 2014).

Site personnel should obtain information from the subject in order to complete this survey. The WPS is a 9-question instrument used to assess [REDACTED]

[REDACTED] One of the WPS questions concerns the [REDACTED]. [REDACTED] will be asked questions about the [REDACTED]; [REDACTED] on a 0 to 10 scale (0=no interference; 10=complete interference). In addition, all subjects regardless of their employment status will be asked questions [REDACTED]

[REDACTED] [REDACTED]; [REDACTED] on a 0 to 10 scale (0=no interference; 10=complete interference).

The WPS assessments per visit are described in Table 5–1.

---

### 9.1.16 Resources utilization

Study-specific questionnaires (standard CRF modules) will be used to capture data regarding resources utilization during the study, ie:

- Concomitant medical procedures
- Health care provider consultations not foreseen by the protocol
- Hospitalizations/emergency room visit

Site personnel should obtain information from the subject and also corroborate data with known AEs and SAEs in order to complete this survey as described in [Table 5–1](#). The recall period for the questionnaire will be the previous 4 weeks.

### 9.1.17 SF-36

The SF-36 (version 2, standard recall) is a 36-item generic HRQoL instrument that uses a recall period of 4 weeks. Items are grouped into 8 domains as follows: Physical Functioning (10 items), Role Physical (4 items), Bodily Pain (2 items), General Health (5 items), Vitality (4 items), Social Functioning (2 items), Role Emotional (3 items), Mental Health (5 items), and 1 item for perceived stability or change in health (Health Transition) during the last year. The concepts represented by these domains contribute to physical, mental, and social aspects of HRQoL.

In addition to domain scores, the PCS and MCS scores are calculated from the 8 domains (excluding the Health Transition item). Component scores appreciate the impact of each domain on physical and mental health status (Ware et al, 1994). Each of the 8 domain scores and the component summary scores range from 0 to 100, with a higher score indicating a better health status. The 2 component summary scores are standardized with a mean of 50 and a standard deviation (SD) of 10 in the general USA population. The MCIDs for SF-36 domains and component summaries are 5 and 2.5 points, respectively (Strand et al, 2005) (see [Appendix 18.10](#)).

The SF-36 has been used and has shown to be responsive in axSpA (Haibel et al, 2008) and is also validated (van Tubergen et al, 2015). The SF-36 will be administered per visit as described in [Table 5–1](#) and [Table 5–2](#).

### 9.1.18 Spinal mobility

In addition to the assessments performed for the BASMI, additional spinal mobility assessments include:

- Occiput to wall distance
- Chest expansion

Spinal mobility will be assessed as described in [Table 5–1](#) and [Table 5–2](#).

### 9.1.19 Swollen and tender joint counts (44 joints evaluation)

The following 44 joints are to be examined for swelling and tenderness by the Principal Investigator, another delegated physician, or an appropriately qualified medical professional (based on local requirements) who has had documented training on how to perform these assessments correctly. Preferably the same assessor should evaluate the subject at each arthritis assessment.

Upper body (4) – bilateral sternoclavicular, and acromioclavicular joints

Upper extremity (26) – bilateral shoulders, elbows, wrists (includes radiocarpal, carpal and carpometacarpal bones considered as a single unit), metacarpophalangeals (MCPs) I, II, III, IV, and V, and thumb interphalangeals (IPs), and proximal IPs (PIPs) II, III, IV, and V

Lower extremity (14) – bilateral knees, ankles, and metatarsophalangeals (I, II, III, IV, and V)

The assessment for swelling and tenderness is made on 44 joints from the above list. Artificial and ankylosed joints are excluded from swelling and tenderness assessments.

The assessments per visit are described in [Table 5–1](#) and [Table 5–2](#).

